2. STATISTICAL HYPOTHESES

Part A:

There will be no formal statistical hypotheses for part A.

The comparison of two 4 mg daprodustat tablets with different dissolution profiles relative to the reference 4 mg daprodustat tablet made by Process 1 will be performed using descriptive statistics. The ratio of the geometric means (μ dissolution 1/ μ Process 1 and μ dissolution 1/ μ Process 2) for AUC(0-t) and Cmax will be calculated and 90% confidence interval (CI) will be generated as part of the descriptive statistics.

Part B:

For each tablet strength of daprodustat (1 mg, 2 mg, 4 mg, 6 mg, and 8 mg), the following statistical hypotheses will be used:

The bioequivalence between daprodustat manufacturing process 1 and process 2 will be assessed using a framework of statistical hypothesis testing. The ratio of the geometric means (μ Process 2 / μ Process 1) for AUC(0-t) and Cmax is the measure in the following statistical hypotheses:

H_0 (null hypothesis) : μ Process 2 / μ Process 1 ≤ 0.80 or μ Process 2 / μ Process 1 ≥ 1.25 ,

H_1 (alternative hypothesis) : $0.80 < \mu$ Process 2 / μ Process 1 < 1.25

Bioequivalence will be determined if the 90% confidence interval (CI) of μ Process 2 / μ Process 1 falls within a range of 0.80 to 1.25. This is equivalent to carrying out two one-sided tests of hypothesis at the 5% level of significance.

A demonstration of bioequivalence requires the null hypothesis for both AUC and Cmax to be rejected. All doses must meet the criteria for bioequivalence to be concluded

2.1. Multiplicity Adjustment

No multiplicity adjustments will be made for the final analysis of the primary endpoint. Although the primary endpoint for Part B will include statistical testing, doses of Part B will be enrolled and analysed independent of each other, therefore no Type I error adjustments will be made. There will be no formal statistical hypotheses for part A.

3. ANALYSIS SETS

The following populations are defined for both Part A and B separately:

Analysis Set	Definition / Criteria	Analyses Evaluated
Screened	
 • All participants who were screened for eligibility 	
 • Study Population
Enrolled	
 • All participants who signed the ICF 	
 • Study Population
Safety	
 • All randomized participants who take at least 1 dose of study intervention. Participants will be analyzed according to the intervention they actually received. 	
 • Study Population, Safety
Pharmacokinetic (PK)	
 • All participants in the Safety population who had at least 1 non-missing PK assessment (Non-quantifiable [NQ] values will be considered as non-missing values). 	
 • PK

4. STATISTICAL ANALYSES

4.1. General Considerations

Pharmacokinetic parameters of daprodustat will be calculated by standard noncompartmental analysis according to current working practices and using the currently supported version of WinNonlin 6.3 or higher. All calculations of non-compartmental parameters will be based on actual sampling times. Pharmacokinetic parameters listed will be determined from the plasma concentration-time data, as data permits.

For both Part A and Part B, the plasma concentrations of daprodustat will be summarized by nominal time and individual plasma concentration-time profiles and median/mean profiles will be plotted. Each of the figures will contain one plot on the untransformed scale (i.e. a linear plot) and one plot on the log transformed scale (i.e. a log-linear plot).

For both Part A and Part B, from the plasma concentration-time data, the following PK parameters: AUC(0-t), AUC(0-inf), Cmax, Tmax, t1/2, CL/F, Vz/F. The bioequivalence between the tablets will be confirmed with comparisons of the values of the logarithmic parameters [AUC(0-t) and Cmax]. The comparison of the difference will be assessed on

the log scale with point estimates exponentiated back to provide geometric mean ratio and associated 90% CI.

Calculations will be based on the actual sampling times recorded during the study. PK data, will be presented in graphical and tabular form and will be summarized descriptively, using summary statistics (n, arithmetic mean with associated 95% CI, standard deviation (SD), minimum, median, and maximum). Except for Tmax, geometric mean with associated 95% CI, SD on loge scale and coefficient of variation between participants (%CVb) will also be provided. Listings will be generated for each derived plasma PK parameters.

4.1.1. General Methodology

All PK analyses will be performed on the PK Population for each Part.

Unless otherwise specified, continuous data will be summarized using descriptive statistics: n, mean, standard deviation (SD), median, minimum and maximum. Categorical data will be summarized as the number and percentage of participants in each category. **Baseline Definition**

For all endpoints the baseline value will be the latest pre-dose assessment with a non-missing value, including those from unscheduled visits. If time is not collected, Day 1 assessments are assumed to be taken prior to first dose and used as baseline.

Parameter	Study Assessments Considered As Baseline			Baseline Used in Data Display
	Screening	Day -1	Day 1 (Pre-Dose)	
Safety				
Haematology	X	X		Day -1
Chemistry	X	X		Day -1
12-lead ECG & Vital	X			Screening
Vital Signs	X	X	X	Day 1 (Pre-dose)

Unless otherwise stated, if baseline data is missing no derivation will be performed and baseline will be set to missing. **Multicenter Studies**

It is anticipated that patient accrual will be spread across centers based on Part A, Part B, and dose and summaries of data by center would unlikely be informative and will not, therefore, be provided. **Primary [Endpoint(s)/Estimand(s)] Analyses**

Part A

Objectives	Endpoints
Primary	

 To characterize single dose PK profile of 4 mg daprodustat tablets with two different 	Area under the concentration-time curve [AUC (0-t)] and Maximum observed

Objectives	Endpoints
dissolution profiles made by Process 2 relative to the reference 4 mg daprodustat tablet made by Process 1	concentration (C_{max}) of daprodustat

Part B

Objectives	Endpoints
Primary 
 • To establish BE between daprodustat tablets made by two different manufacturing processes, Process 1 and Process 2, for the following dose strengths administered as a single dose: 
 • 1 mg • 2 mg • 4 mg • 6 mg • 8 mg 	AUC (0-t) and C_{max} of daprodustat

4.2.1. Definition of endpoint(s)

The primary objective of Part A is to characterize the PK profile of two 4 mg daprodustat tablets with different dissolution profiles relative to the reference 4 mg daprodustat tablet made by Process 1.

Part B will have one primary objective and two endpoints, AUC (0-t) and Cmax.

The primary objective of Part B is to assess the bioequivalence between manufacturing Process 1 and Process 2 for the following tablet strengths: 1 mg, 2 mg, 4 mg, 6 mg, 8 mg.

Parameter	Parameter Description
AUC(0-t) (h^*ng/mL)	The area under the concentration-time curve from zero time (pre-dose) to the time of last quantifiable concentration (AUC(0-t)) will be calculated by a

Parameter	Parameter Description
	combination of linear and logarithmic trapezoidal methods. The linear trapezoidal method will be employed for all incremental trapezoids arising from increasing concentrations and the logarithmic trapezoidal method will be used for those arising from decreasing concentrations (i.e., Linear Up/Log Down calculation method in Phoenix WinNonlin Professional).
Cmax (ng/mL)	Maximum observed plasma concentration following each dose will be obtained directly from the concentration-time data.

4.2.2. Main analytical approach

Endpoint / Variables
Part A: AUC (0-t) and C _{max} of daprodustat
Part B: AUC (0-t) and C _{max} of daprodustat
Model Specification
Part A: For Part A the following statistical analysis method will be used: The exposure [AUC(0-t) and C _{max}] of daprodustat will be assessed by using a mixed effect model as described below: $\text{log}_e (\text{PK parameter}) = \beta_0 + \gamma_i + \tau_j + \pi_k + \epsilon_{ijkl}$ where β_0 is the intercept, γ_i is the random participant effect for ith participant, τ_j is the tablet manufacturing effect (j = dissolution 1, dissolution 2, Process 1), π_k is the period effect (k = period 1, period 2, period 3), and ϵ_{ijkl} is the random error. The model parameters will be estimated using Restricted Maximum Likelihood with the Newton-Raphson algorithm. The Kenward-Roger degree of freedom approach will be used. Given the random effect for subject i, the random error is assumed to be independently distributed within the subject. Point estimates, $\log_e \mu$, for the model-based means of PK parameters on loge scale will be provided for dissolution 1, dissolution 2, and Process 1 and a point estimate of the mean difference between comparisons ($\log_e \mu$ dissolution 1, 2 - $\log_e \mu$ Process 1) will be constructed along with the associated 90% CIs using the residual variances. The point estimates, the point estimate of the mean difference, and the associated 90% CIs on loge scale will be exponentially back-transformed to obtain the model-based

geometric means (μ), and the ratio for AUC(0-t) and Cmax (μ dissolution 1/ μ Process 1 and μ dissolution 1/ μ Process 2) and the associated 90% CIs, respectively.

Within-subject variability (%CVw) for the PK parameters will be estimated using within-subject variance from the analysis model as follows:

$$\%CVw (\%) = [\exp(\sigma_w^2) - 1]^{1/2} \times 100$$

AUC(0-inf) will be analyzed in the same manner.

Part B:

For each tablet strength of daprodustat (1 mg, 2 mg, 4 mg, 6 mg, and 8 mg), the following statistical analysis method will be used (separate model for each dose strength):

The exposure (AUC(0-t) and Cmax) of daprodustat will be assessed by using a mixed effect model as described below:

$$\log_e (\text{PK parameter}) = \beta_0 + \gamma_i + \tau_j + \pi_k + \varepsilon_{ijkl}$$

where β_0 is the intercept, γ_i is the random participant effect for i th participant, τ_j is the tablet manufacturing effect (j = Process 1 or Process 2), π_k is the period effect (k = period 1 or period 2), and ε_{ijkl} is the random error.

The model parameters will be estimated using Restricted Maximum Likelihood with the Newton-Raphson algorithm.

The Kenward-Roger degree of freedom approach will be used.

Given the random effect for subject i , the random error is assumed to be independently distributed within the subject.

Point estimates $\log_e \mu$, for the model-based means of PK parameters on loge scale will be provided for each tablet strength and a point estimate of the mean difference between processes ($\log_e \mu$ Process 2 - $\log_e \mu$ Process 1) will be constructed along with the associated 90% CIs using the residual variances. The point estimates, the point estimate of the mean difference, and the associated 90% CIs on loge scale will be exponentially back-transformed to obtain the model-based geometric means (μ), and the ratio for AUC(0-t) and Cmax (μ Process 2 / μ Process 1) and the associated 90% CIs, respectively.

Bioequivalence will be evaluated using the FDA BE guidelines, Criterion 1. It is noted that if Criterion 1 fails, the next step per Japan BE guidance is Criterion 2. However, the study design is based on Criterion 1 given its more stringent criteria

- Criterion 1:

The 90% CIs of the ratios of the geometric means for AUC(0-t) and Cmax (μ Process 2 / μ Process 1) are within the range of 0.80 - 1.25.

- Criterion 2

The ratio of the geometric means for AUC(0-t) and Cmax (μ Process 2 / μ Process 1) is within the range of 0.90 - 1.11.

Within-subject variability (%CVw) for the PK parameters will be estimated using within-subject variance from the analysis model as follows:

$$\%CVw (\%) = [\exp(\sigma_w^2) - 1]^{1/2} \times 100$$

AUC(0-t) will be analyzed in the same manner.

Model Checking & Diagnostics

- In case there is a problem with model convergence, the arithmetic means for loge-transformed AUC(0-t) and Cmax and the treatment differences within each subject will be calculated using only data from the subjects who have completed all periods. The mean treatment difference and paired-t test based 90% CIs for treatment difference in loge scale will be estimated. The results will be provided in an exponentially back-transformed scale.
- This will be done for both Part A and Part B.

Model Results Presentation

- Results of Part A and Part B will be presented in the same manner, separately.
- The estimates of geometric means of PK parameters (AUC(0-t) and Cmax) will be presented for each dissolution profile and Process 1 (Part A) or for Process 1 and 2 for each tablet strength (Part B), respectively. The estimates of the geometric means ratio between each dissolution profile and Process 1 (Part A) or between Process 1 and 2 (Part B) will be presented along with the associated 90% CIs and %CVw.
- AUC(0-t) will also be provided in the model results presentation, but the evaluation of the bioequivalence for Part B will not be done based on AUC(0-t).

Model Results Interpretation

Part A:

- There will be no formal statistical hypotheses for part A.

Part B:

- Bioequivalence will be determined if the 90% confidence interval (CI) of μ Process 2 / μ Process 1 falls within a range of 0.80 to 1.25. This is equivalent to carrying out two one-sided tests of hypothesis at the 5% level of significance.
- A demonstration of bioequivalence requires the null hypothesis for both AUC and Cmax to be rejected. All doses must meet the criteria for bioequivalence to be concluded.

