1.1.2. Estimands

Objective	Estimand Category	Estimand		Population Level Summary Measure
		Variable/End point	Intercurrent Event Strategy	
Part A Primary Objective: To characterize single dose PK profile of 4 mg daprodustat tablets with two different dissolution profiles made by Process 2 relative to the reference 4 mg daprodustat tablet made by Process	Primary, Part A	AUC (0-t) and Cmax of daprodustat	Intercurrent events: Treatment discontinuation While-on-treatment strategy - all available data up until the treatment discontinuation will be analysed. (Interest is in the treatment effect prior to the withdrawal). Subjects' data available up to the treatment discontinuation will be included in the descriptive PK summaries. If a subject discontinues treatment during a period, the missing data post withdrawal will not be imputed. The derived PK parameters for e.g., AUC, Cmax etc. of that partially completed period will be calculated, if data permits.	1) Descriptive statistics (Section REF Ref54661353 \n \h 4.3.2)(2) Treatment Ratios (Section REF Ref518462394 \n \h 4.2.2)
Part B Primary Objective: To establish BE between daprodustat tablets made by two different manufacturing processes, Process 1 and Process 2, for the following dose	Primary, Part B	AUC (0-t) and Cmax of daprodustat	Intercurrent events: Treatment discontinuation While-on-treatment strategy - all available data up until the treatment discontinuation will be analysed. (Interest is in the treatment effect prior to the withdrawal). Subjects' data available up to the treatment discontinuation will be included in the descriptive PK summaries. If a subject discontinues treatment during a period, the missing data post withdrawal will not be imputed. The derived PK parameters for e.g., AUC,	(1) Descriptive statistics (Section REF Ref54661353 \n \h 4.3.2)(2) Treatment Ratios (Section REF Ref518462394 \n \h 4.2.2)

Objective	Estimand Category	Estimand		
		Variable/End point	Intercurrent Event Strategy	Population Level Summary Measure
strengths administered as a single dose: 
• 1 mg• 2 mg• 4 mg• 6 mg• 8 mg			Cmax etc. of that partially completed period will be calculated, if data permits.	

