4.2.3. Sensitivity analyses

A sensitivity analysis to jointly assess BE across all doses will be performed on Part B using a statistical model incorporating all doses used in Part B if at least one dose fails to achieve BE in Part B.

Model Specification

 • $\log_e (\text{PK parameter}) = \beta_0 + S_i + \beta_1 * \log(\text{dose}) + \beta_2 * F + \beta_3 * F * \log(\text{dose}) + \epsilon_j$ 
 ○ β_0 is the Intercept of reference; β_1 is the main effect for dose for reference (slope); β_2 is the difference of intercept between the two formulations; β_3 is the difference of slope between the two formulations ○ Dose: 1, 2, 4, 6, or 8 mg; F: manufacturing process (process 1 or process 2) ○ S_i is the random effect for subject I; ϵ_j is the random error • Model based comparison for each dose 
 ○ For each dose, a contrast statement will provide the estimate and 90% CI, these will be used to evaluate BE: 
 ■ The 90% CIs of the ratios of the geometric means for $AUC(0-t)$ and C_{max} (μ Process 2 / μ Process 1) are within the range of 0.80 - 1.25. ○ This model will incorporate all 5 doses within one model
Model Checking & Diagnostics

 • In case there is a problem with model convergence, the arithmetic means for loge-transformed $AUC(0-t)$ and C_{max} and the treatment differences within each subject will be calculated using only data from the subjects who have completed all periods. The mean treatment difference and paired-t test based 90% CIs for treatment difference in loge scale will be estimated. The results will be provided in an exponentially back-transformed scale.
Model Results Presentation

 • The estimates of the geometric means ratio between Process 1 and 2 (Part B) will be presented along with the associated 90% CIs and %CVw.

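### If the primary mixed model does not converge, the SAP falls back on a completers-only paired t-test that omits the period effect; a least-squares ANOVA would keep it at no cost

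*SAP*

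**What the plan says.** SAP 4.2.2 gives one mixed model per part. The period term π_k is a fixed effect in both. In Part A it "is the period effect (k = period 1, period 2, period 3"; in Part B it "is the period effect (k = period 1 or period 2". Estimation is by REML.

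Under Model Checking & Diagnostics, the same section covers failed convergence. Log-scale means and within-participant treatment differences "will be calculated using only data from the subjects who have completed all periods". Then: "The mean treatment difference and paired-t test based 90% CIs for treatment difference in loge scale will be estimated". On scope it adds: "This will be done for both Part A and Part B". No period or sequence term is named.

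SAP 1.1.2 describes the handling of treatment discontinuation differently: "all available data up until the treatment discontinuation will be analysed".

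SAP 4.2.3 repeats the fallback, again "using only data from the subjects who have completed all periods", for the joint model across strengths. That model is run only if at least one strength fails bioequivalence. Protocol 9.4.2 contains no fallback, so the SAP text is the only rule.

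**The concern.** The primary models adjust for period because a shift between dosing occasions would otherwise enter the treatment comparison. The fallback removes that adjustment in the one situation where it replaces the primary model. In a two-period crossover, a period shift moves the within-participant differences of the two sequences in opposite directions. Averaged without regard to sequence, those shifts cancel only if the sequences are equal in size. Even when they cancel in the mean, they stay in the spread and widen the interval.

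In Part B the fallback CI would decide bioequivalence for that strength, and all five strengths must pass. Part A has no formal hypothesis, so only the precision and description of the two ratios are affected there.

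**Working it through.** **Inputs from the documents.** CVw is 25% for Cmax and 19% for AUC, the true ratio is 1.0, there are 38 completers per strength (19 per sequence) and 30 in Part A (10 per sequence), and the dropout rate is 10% in Part B (SAP 5). The limits are 0.80 to 1.25 with a 90% CI (SAP 2). Part B randomizes 210 (Protocol 5), which is 42 per strength and 21 per sequence at 1:1.

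**Assumptions.** The documents give no period effect and no completer split other than the planned one. Period effects of 10% and 20% and unequal splits are assumed below.

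**The plan's own figures first.**
- σw² = ln(1 + 0.25²) = 0.0606.
- Part B: SE = √(2 × 0.0606/38) = 0.0565. With t(0.95, 36) = 1.688 the half-width is 0.0954, so the CI at a ratio of 1.0 is 0.909 to 1.100.
- Exact power of the two one-sided tests is 97.4% for Cmax (stated 97%) and 99.94% for AUC (stated above 99%). Global power is (0.9742 × 0.9994)^5 = 87.5% (stated 87%).
- Part A: t(0.95, 56) × √(2 × 0.0606/30) = 0.106, so the CI is 0.899 to 1.112 (stated 0.90 to 1.11).

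The stated figures reproduce. They describe the period-adjusted analysis.

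**The fallback in Part B.** Let D be the log period effect and n1, n2 the completers per sequence, with N = n1 + n2.
- Bias of the paired mean, in size: D × (n1 − n2)/N.
- Expected variance of the differences: 2σw² + D² × 4n1n2/[N(N − 1)], on N − 1 df.

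*19:19, 20% period effect.* The bias is zero. D² = (ln 1.20)² = 0.0332. The variance is 0.1213 + 0.0332 × 1444/1406 = 0.1554. The SE is √(0.1554/38) = 0.0639, and the half-width is 1.687 × 0.0639 = 0.1079. Against 0.0954 this is 1.13 times as wide.

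*21:17, 10% period effect.* The bias is ln(1.10) × 4/38 = 0.0100, about 1.0% of the ratio.

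Power and false-bioequivalence rates come from 200,000 simulated trials per case:

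| Split, period effect | Bias in ratio | CI width against period-adjusted | Power, fallback / adjusted | False-BE rate of fallback, worse / better margin |
|---|---|---|---|---|
| 19:19, none | 0 | 1.00 | 97.5% / 97.5% | 5.0% / 5.0% |
| 19:19, 10% | 0 | 1.04 | 96.9% / 97.4% | 4.5% / 4.4% |
| 19:19, 20% | 0 | 1.13 | 95.5% / 97.4% | 3.2% / 3.2% |
| 21:17, 10% | 1.0% | 1.03 | 96.8% / 97.3% | 6.3% / 3.1% |

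The period-adjusted analysis stays near 5% at both margins in every row.

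**Part A.** The three sequences form a Latin square, so at 10:10:10 the period terms cancel exactly in both ratios. At an assumed 12:10:8 with period ratios 1/1.05/1.10, each ratio is multiplied by about 0.990. With no period effect the fallback CI is 1.016 times as wide, because it uses 29 df instead of 56.

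**The alternative.** On a simulated complete 2×2 data set with 21:17 sequences, REML and least squares with fixed participant effects both gave −0.02736 (SE 0.05644). The paired mean gave −0.03724.

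**The case against.** The strongest case against is that the trigger is remote. The Part B model is a random intercept with two two-level factors and about 38 participants. A non-iterative fallback is already prespecified, so nobody chooses a method after seeing the data. The planned 1:1 allocation makes the bias zero in both parts. A 21:17 split with no replacement needs all four dropouts in one sequence. The higher error rate applies to one margin only; the other becomes more conservative. All of this stands, and it is why the priority is low.

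Planned balance is not guaranteed balance, however. If each of 21 participants per sequence drops out independently with probability 10% and none is replaced (assumed), a strength ends with unequal sequences 79% of the time. At least one of five strengths then differs by four or more completers about 30% of the time. SAP 5 allows replacement but does not say that it keeps the sequence.

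Three stronger readings are tempting, and the documents do not support them.
- A reader might infer that the fallback always gives a biased ratio and a CI of the wrong width. Bias needs both a period effect and unequal completers, and with no period effect the CI is valid.
- A reader might infer that the joint-model fallback in SAP 4.2.3 loses a period effect and the dose effect. That model lists no period term. Each Part B participant receives one strength, so log(dose) cancels in every within-participant difference. Run by dose, the fallback still gives a ratio and CI per strength, though without the common slope across doses. What is left is that 4.2.3 does not say whether the differences are taken by dose or pooled.
- A reader might infer that the restriction to completers costs information in Part B. A participant with one period has no within-participant contrast, and the ANOVA proposed here gives that participant no weight on the ratio either.

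**Conclusion.** The point holds as a minor gap in SAP 4.2.2: the fallback omits a term that both primary models include, and a better non-iterative method exists. The effect on Part B is modest: about a 1% shift in the ratio, or a CI about 13% too wide, in the assumed cases above. Those sizes rest on assumed period effects and, for the bias, an assumed unequal split. They matter only if the model fails to converge, for which no probability can be taken from the documents.

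The conflict with the all-available-data statement in SAP 1.1.2 has force only in Part A. There, a participant with both the test and the reference period is discarded for missing the third. Part A makes no bioequivalence decision, so the loss is one of precision.

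**What to change.** In SAP 4.2.2, replace the fallback for both parts with a least-squares ANOVA: log(parameter) = participant + period + treatment, all fixed, using all available periods, with the 90% CI from the residual mean square. It has a closed-form solution and cannot fail to converge. With complete data it gives the same treatment estimate as the mixed model. In Part A it keeps participants who have two of the three periods, and it pools the residual variance over all three treatments.

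In SAP 4.2.3, state that the joint-model fallback is run by dose.

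The cost is one replaced sentence and one clarification before database lock. Sample size, data collection and the primary models are unchanged, and the protocol contains no fallback text to amend.

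### The SAP excludes AUC(0-t), a co-primary endpoint, from the Part B bioequivalence evaluation, contradicting its own decision rule

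*SAP*

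**What the plan says.** Most of the plan gives one rule for Part B: AUC(0-t) and Cmax must both pass, at every strength.

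- SAP 4.2.1: "Part B will have one primary objective and two endpoints, AUC (0-t) and Cmax".
- SAP 4.1 bases the bioequivalence conclusion on "values of the logarithmic parameters [AUC(0-t) and Cmax"; Protocol 9.4.1 does the same.
- SAP 4.2.2, Criterion 1: "The 90% CIs of the ratios of the geometric means for AUC(0-t) and Cmax" must lie within 0.80-1.25.
- SAP 2, repeated under Model Results Interpretation in 4.2.2: "A demonstration of bioequivalence requires the null hypothesis for both AUC and Cmax to be rejected".
- SAP 4.2.2 then adds: "All doses must meet the criteria for bioequivalence to be concluded".

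Two sentences in the Part B text of SAP 4.2.2 do not fit.

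- The model specification ends with "AUC(0-t) will be analyzed in the same manner". At the same point, Part A has "AUC(0-inf) will be analyzed in the same manner".
- The third bullet of Model Results Presentation says that AUC(0-t) will also be shown, but that "the evaluation of the bioequivalence for Part B will not be done based on AUC(0-t".

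**The concern.** The third bullet removes from the decision a parameter that the same section requires to pass. Taken literally, it leaves Cmax as the only named parameter that decides bioequivalence. A process change that moved total exposure to or beyond a limit could then be declared bioequivalent, provided peak concentration held.

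The SAP is the document that programmers and report authors will follow. A primary decision rule that can be read in two ways also leaves room to choose between the readings after the data are seen.

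There is a smaller consequence. As written, the SAP models the AUC(0-inf) ratio in Part A but not in Part B, where AUC(0-inf) gets descriptive statistics only (SAP 4.3.2).

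**Working it through.** **1. What the text supports**

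AUC(0-t) is a Part B bioequivalence parameter in the SAP objectives (1.1.1), estimands (1.1.2), hypotheses (2), general considerations (4.1), endpoint definitions (4.2.1), Criterion 1 (4.2.2), sensitivity analysis (4.2.3) and power statement (5). The protocol agrees in 9.1, 9.2, 9.4.1 and 9.4.2. SAP 5 counts 10 confidence intervals, which is 5 strengths × 2 parameters. SAP 4.6 declares no change from the protocol.

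Both odd sentences are also redundant as they stand. The Part B model already covers AUC(0-t), so there is nothing left to analyse in the same way. The bullet before the contested one already presents AUC(0-t), so it cannot *also* be provided. Both sentences make sense if the parameter is AUC(0-inf), a secondary endpoint, as in Part A.

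**2. Inputs (SAP 5, same as Protocol 9.2)**

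- n = 38 completers per strength in a 2×2 crossover, so df = 36
- CVw 25% for Cmax and 19% for AUC
- limits 0.80-1.25, with two one-sided 5% tests
- planned true ratio 1.0

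**3. Formulas**

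- σw = √ln(1 + CV²)
- SE = σw·√(2/n)
- A strength passes on one parameter if |log ratio estimate| + t(0.95, 36)·(estimated SE) < ln 1.25, with t = 1.688 and ln 1.25 = 0.2231.
- The pass probability is integrated over the chi-square distribution of the residual variance.

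Cmax: σw = 0.2462, SE = 0.0565. AUC: σw = 0.1883, SE = 0.0432.

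**4. The plan's own figures**

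| Quantity | Stated | Recomputed |
|---|---|---|
| Cmax power per strength, ratio 1.00 | 97% | 97.4% |
| AUC power per strength, ratio 1.00 | >99% | 99.94% |
| Global power, both parameters: (0.9742 × 0.9994)^5 | 87% | 87.5% |
| Global power, Cmax alone: 0.9742^5 | not given | 87.8% |

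The global figures treat strengths and parameters as independent. Simulation with an AUC-Cmax correlation of 0 to 0.8 gives 87.4% to 87.8% for the two-parameter rule. The stated 87% fits either rule, so it cannot show which was meant. The count of 10 intervals can.

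**5. What dropping AUC(0-t) would do**

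Take a strength whose true AUC ratio is at the limit, 1.25. Its AUC test passes with probability 5.0%, so a rule needing both parameters passes at most 5%. On Cmax alone:

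| Assumed true Cmax ratio | That strength passes | All five pass, every strength at this Cmax ratio |
|---|---|---|
| 1.00 | 97.4% | 88% |
| 1.05 | 91.6% | 64% |
| 1.10 | 71.7% | 19% |
| 1.15 | 42.2% | 1% |

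The last column is the fifth power of the column before it, for example 0.916^5 = 0.64.

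If only one strength has an AUC ratio of 1.25 and every Cmax ratio is 1.00, the whole study still passes on Cmax alone with probability 0.9742^5 = 88%. If that one strength has a Cmax ratio of 1.15 and the other four are at 1.00, the figure is 0.422 × 0.9742^4 = 38%.

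**The case against.** The strongest reply is that nobody would follow the bullet. It sits under a presentation heading, the correct rule comes directly below it, and AUC(0-t) is named as a bioequivalence parameter throughout both documents. This stands as an account of the cause: it is very probably a slip and not a change of rule. It does not make the sentence harmless, because the sentence speaks directly to the primary decision and says the opposite of the rule.

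A second reply is that the rule in SAP 2 and 4.2.2 says AUC without a suffix, so excluding AUC(0-t) might leave AUC(0-inf) with Cmax, and total exposure would still be tested. This is possible on the words but weak, since no part of either document makes AUC(0-inf) a bioequivalence parameter.

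A third reply is that the illustration is extreme. An AUC ratio at the limit with Cmax near 1.00 is a boundary case, and nothing in the documents suggests it is expected. At study level the risk falls quickly if Cmax shifts at every strength. Both points are fair, and the figures show what the AUC test protects against, not what is likely to happen.

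Finally, Protocol 9.4.3 plans only summary statistics for AUC(0-inf), so the lack of a modelled Part B ratio is not in itself a departure from the protocol. That is correct, and the point is minor.

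**Conclusion.** The concern holds and must be fixed. SAP 4.2.2 excludes a co-primary endpoint from the decision that the same section says depends on it. Sample size and stated power are sound under either reading.

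The damage is to the control of false claims: for a strength with a true AUC ratio of 1.25, the chance of passing rises from at most 5% to between 42% and 97%. This rests on the plan's CVs and sample size, and on assumed true Cmax ratios of 1.15 down to 1.00. That AUC(0-inf) was intended is a strong inference from the Part A wording and from the redundancy of the Part B sentences. Neither document states it.

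**What to change.** The sponsor should confirm the intended parameter and amend SAP 4.2.2 before Part B is unblinded:

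- In the closing sentence of the Part B model specification, replace AUC(0-t) with AUC(0-inf), to match Part A.
- In the third bullet of Model Results Presentation, replace both mentions of AUC(0-t) with AUC(0-inf). AUC(0-inf) is then presented as supportive and does not decide bioequivalence.
- Leave AUC(0-t) and Cmax as the two deciding parameters. It would also help to write AUC(0-t) in place of the bare AUC in the decision rule in SAP 2 and 4.2.2.

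The essential change is three mentions of one parameter name. It needs no extra data, participants or sample size work. It does add a modelled AUC(0-inf) ratio for Part B, in line with Part A.
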